7.4.2. Subject Withdrawal Criteria

Participation in the study is strictly voluntary. Subjects have the right to withdraw from study drug or from the study at any time and for any reason. A subject's participation may be terminated for any of the reasons delineated in Section 7.4.1. Whenever possible, the investigator will consult with the sponsor medical monitor before halting a subject's participation in the study.

Although a subject may withdraw from the study at any time without specifying a reason for withdrawal, the reason for withdrawal, if provided by the subject, will be recorded in the

subject's medical records (source documents) and also in the eCRF. If the reason for subject withdrawal is not known, attempts to contact the subject must be documented to establish whether the reason was due to an AE, and if so, this must be reported in accordance with the procedures outlined in Section 7.4.1 and Section 13.4. Vigorous attempts will be made for follow-up of all subjects who miss a study visit. If at any point in the study the clinic is unable to contact the subject after appropriate attempts have been made, the subject will be considered lost to follow-up. If a subject's participation in this study is terminated, the responsible investigator/clinical staff member will document termination in the source documents.

Once subjects have withdrawn from the study, the sponsor will no longer provide treatment through the study.

7.4.3. Criteria for Study Termination

The following study stopping criteria will be used to stop the study (permanent termination or suspension of enrollment/treatment) or the participation of a particular investigational site:

- Emergence of unacceptable risk, toxicity, or negative change in the benefit-risk assessment
- In the event that 3 subjects are determined by the NRMWG to have confirmed elevations of $sCr \ge 3 \times ULN$ considered related to BCX9930
- Request of the relevant competent authority or ethics committee
- Non-compliance with the study protocol, including inaccurate or incomplete recordkeeping, that jeopardizes the scientific integrity of the study or subject safety

BioCryst reserves the right to discontinue the study prior to inclusion of the planned number of subjects but intends to exercise this right only for valid scientific or administrative reasons. If BioCryst does discontinue the study, the investigator must contact all participating subjects immediately after notification of study termination.

7.4.4. End of Study Definition

The end of the study will be defined as the date when the last subject completes the last protocol-scheduled visit.

8. SELECTION AND WITHDRAWAL OF SUBJECTS

8.1. Subject Inclusion Criteria

Subjects must meet all of the following inclusion criteria (where applicable) prior to first dose of BCX9930 on Day 1 or specified time below:

- 1. Willing and able to provide written informed consent (or, for subjects who have not reached the age of maturity, willing and able to provide written assent with written informed consent additionally provided by the subject's parent[s] or legal guardian).
- 2. Male or non-pregnant, non-lactating female subjects \geq 18 years of age.
- 3. Body weight \geq 40 kg.

- 4. Primary diagnosis of C3G, IgAN, or PMN with evidence of disease activity, as confirmed by central pathology review of digital images and pathology reports of renal biopsy samples obtained during screening as described in Section 12.4.2.1 (or within 3 months prior to screening for subjects with C3G and 6 months prior to screening for subjects with IgAN and PMN with approval of the central pathologist and agreement with the medical monitor).
 - All: $\leq 50\%$ global glomerulosclerosis
 - All: < 50% tubulointerstitial fibrosis
- 5. For subjects with C3G only, documentation of duration of illness of at least 90 days by either a prior biopsy collected ≥ 90 days prior to screening confirming a diagnosis of C3G OR a clinical diagnosis of C3G with at least one documented proteinuria assessment ≥ 90 days prior to initial screening visit.
- 6. For subjects with C3G only, proteinuria defined as ≥ 1 g of urinary protein per 24 hours at screening that has not shown a $\geq 25\%$ decrease from the most recent documented proteinuria assessment, which was collected at least 30 days prior to and within 180 days of initial screening visit.
- 7. For subjects with IgAN only, proteinuria defined as 1 g to ≤ 4 g of urinary protein per 24 hours at screening that has not shown a ≥ 25% decrease from the most recent documented proteinuria assessment, which was collected at least 30 days prior to and within 180 days of initial screening visit.
- 8. For subjects with PMN only, an of ≥ 150 U/mL and 3.5 g to ≤ 11 g of urinary protein per 24 hours at screening that has not shown a $\geq 25\%$ decrease from the most recent documented proteinuria assessment, which was collected ≥ 30 days prior to and ≤ 180 days of initial screening visit.
- 9. An eGFR ≥ 50 mL/min/1.73 m² (or ≥ 30 mL/min/1.73 m² after DMC recommendation) calculated using the serum creatinine-based Chronic Kidney Disease Epidemiology Collaboration (CKD-EPI) formula.
- 10. Resting supine vital signs within the following ranges:
 - Systolic blood pressure, 80 to 150 mm Hg, inclusive
 - Diastolic blood pressure ≤ 90 mm Hg
- 11. Treatment with a stable, maximum recommended or maximum tolerated dose of an angiotensin-converting enzyme inhibitor (ACEi) or angiotensin receptor blocker (ARB) for at least 60 days prior to the Day 1 Visit and in the opinion of the investigator the expectation of continuing the same dose and regimen for such treatment during the study.
- 12. Contraception requirements:

Female subjects must meet at least one of the following requirements:

a. Be a woman of nonchildbearing potential, defined as postmenopausal (without menses for ≥ 12 months [without an alternative medical cause] with a follicle-

- stimulating hormone [FSH] > 40 mIU/mL, or who have had a hysterectomy, bilateral salpingectomy, or bilateral oophorectomy).
- b. Be a woman of childbearing potential (defined as a female following menarche and prior to becoming post-menopausal who has not had a hysterectomy, bilateral salpingectomy, or bilateral oophorectomy) who agrees to use a highly effective contraceptive method while enrolled in the study and for a duration of 30 days after last dose of study drug. The following methods are acceptable:
 - surgical sterilization (ie, bilateral tubal occlusion or vasectomy of the sole male partner and the vasectomized partner has received medical assessment of surgical success)
 - intrauterine device (IUD) or intrauterine system (IUS)
 - Combined (estrogen and progestogen containing) hormonal contraception associated with inhibition of ovulation (oral, intravaginal, transdermal)
 - Progestogen only hormonal contraception associated with inhibition of ovulation (oral, injectable, implantable)
- c. Women of childbearing potential who declare themselves sexually abstinent or exclusively having female sexual partners do not need to use highly effective contraception. Abstinence in this study is defined as true abstinence, when it is in line with the subject's preferred and usual lifestyle. If a subject is usually not sexually active but becomes active, she, with her partner, must meet the requirements listed above.

Male subjects must meet at least one the following requirements:

- d. Subjects with female partners of childbearing potential (defined as without menses ≤ 12 months, or a non-menopausal female who has not had a hysterectomy, bilateral salpingectomy, or bilateral oophorectomy) must agree to utilize a contraceptive method throughout the study and for at least 90 days after the last dose of study drug. The following methods during the study are acceptable:
 - surgical sterilization (ie, vasectomy that has been medically assessed to be successful, or bilateral tubal occlusion of a female partner)
 - partner's use of an IUD or IUS
 - partner's use of combined (estrogen and progestogen containing) hormonal contraception associated with inhibition of ovulation (oral, intravaginal, transdermal)
 - partner's use of progestogen only hormonal contraception associated with inhibition of ovulation (oral, injectable, implantable)
 - use of a condom
- 13. Documentation of current vaccinations against *N. meningitidis* Types A, C, W, and Y, and *S. pneumoniae* vaccine, or must be vaccinated or willingness to start vaccination series for any of the missing protocol required vaccines at least 14 days prior to Day 1 per Section 12.2.1.

(Note: Vaccination for *N. meningitidis* Type B and for *H. influenzae* Type B (Hib) is strongly encouraged where authorized and available.)

14. In the opinion of the investigator, the subject is likely to comply adequately with all required study procedures and restrictions for the study, including compliance with the BID dosing schedule for BCX9930.

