 - surgical sterilization (ie, bilateral tubal occlusion or vasectomy of the sole male partner and the vasectomized partner has received medical assessment of surgical success)
 - intrauterine device (IUD) or intrauterine system (IUS)
 - Combined (estrogen and progestogen containing) hormonal contraception associated with inhibition of ovulation (oral, intravaginal, transdermal)
 - Progestogen-only hormonal contraception associated with inhibition of ovulation (oral, injectable, implantable)
- c. Women of childbearing potential who declare themselves sexually abstinent or exclusively having female sexual partners do not need to use highly effective contraception. Abstinence in this study is defined as true abstinence, when it is in line with the subject's preferred and usual lifestyle. If a subject is usually not sexually active but becomes active, she, with her partner, must meet the requirements listed above.

Male subjects must meet at least one the following requirements:

d. Subjects with female partners of childbearing potential (defined as without menses ≤ 12 months, or a non-menopausal female who has not had a hysterectomy, bilateral salpingectomy, or bilateral oophorectomy) must agree to utilize a contraceptive method

throughout the study and for at least 90 days after the last dose of study drug. The following methods during the study are acceptable:

- surgical sterilization (ie, vasectomy that has been medically assessed to be successful, or bilateral tubal occlusion of a female partner)
- partner's use of an IUD or IUS
- partner's use of combined (estrogen and progestogen containing) hormonal contraception associated with inhibition of ovulation (oral, intravaginal, transdermal)
- partner's use of progestogen-only hormonal contraception associated with inhibition of ovulation (oral, injectable, implantable)
- use of a condom
- 13. Documentation of current vaccinations against *Neisseria meningitidis* Types A, C, W, and Y, and *Streptococcus pneumoniae*, or willingness to start vaccination series at least 14 days prior to Day 1.

(Note: Vaccination for *N. meningitidis Type B* and for *Hemophilus influenzae* [Hib] is strongly encouraged, where authorized and available.)

14. In the opinion of the investigator, the subject is likely to comply adequately with all required study procedures and restrictions for the study, including compliance with the BID dosing schedule for BCX9930.

Exclusion Criteria:

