5.5.1. Potential Risks of Bacterial Infections

The most significant risk associated with complement inhibitor therapies, including the approved therapies eculizumab or ravulizumab, is the risk of life-threatening or fatal meningococcal infections (Figueroa and Densen 1991, Hillmen, Young et al. 2006). This risk is well known and included as a warning in relevant labels for both Soliris® (eculizumab) and Ultomiris® (ravulizumab) (Alexion Pharmaceuticals 2020, Alexion Pharmaceuticals 2021).

As BCX9930 blocks the AP of complement, subjects may have increased susceptibility to bacterial infections, especially infections with encapsulated organisms, such as *Neisseria meningitidis*, *Streptococcus pneumoniae*, and *Haemophilus influenzae*, but also with unencapsulated strains of *Neisseria meningitidis* and other bacteria such as *Neisseria gonorrhoeae* (Ram, Lewis et al. 2010). Study subjects receiving BCX9930 will be monitored closely for signs and symptoms of infection, and infection risk will be mitigated by requiring subjects to have up-to-date vaccinations against appropriate bacterial strains. If required on an individual basis, prophylactic antibiotic administration will be allowed.

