12.2.1. Vaccination Requirements

BCX9930 blocks the alternative pathway of complement activation; therefore, subjects may have increased susceptibility to bacterial infections, especially infections with encapsulated organisms such as *N. meningitidis*, *S. pneumoniae*, and *H. influenzae*, but also with unencapsulated strains of *N. meningitidis* and other bacteria such as *N. gonorrhoeae*. Effective and current vaccination coverage must be documented for *N. meningitidis* Types A, C, W, and Y, and for *S. pneumoniae*. Vaccination for *N. meningitidis* Type B and for *H. influenzae* (Hib) is strongly encouraged where authorized and available.

For those who have not received all of the required vaccines (including boosters) or vaccine series, administration of any needed vaccines should start no later than 14 days prior to Day 1. If the recommended vaccination coverage requires more than a single dose, then the additional dose(s) may be administered after Day 1 to complete the recommended vaccination coverage. If a vaccine is not available, the sponsor medical monitor (or designee) should be contacted to discuss potential options in order to satisfy eligibility requirements prior to completing the Day 1 visit. Appropriate antibiotics for prophylaxis may be given during the study in accordance with local standard of care and any relevant vaccination guidance (see Section 9.1).

Unless local guidelines are more stringent, the Advisory Committee on Immunization Practices (ACIP) recommendations for meningococcal vaccination and ACIP guidance for altered immunocompetence (including complement inhibition therapy) should be followed (Mbaeyi, Pondo et al. 2020). For vaccines against serogroups A, C, W, and Y, a booster vaccine should be given every 5 years while on complement inhibitor therapy; the available vaccines are interchangeable. For vaccines against serogroup B, a booster vaccine should be given 1 year after the series completion and every 2 to 3 years thereafter; the available vaccines are not interchangeable (Mbaeyi, Pondo et al. 2020).

S. pneumoniae vaccination is also required; vaccination with both conjugate and polysaccharide vaccines is preferred.

Vaccination or a booster vaccine against Hib is strongly encouraged for all study participants where authorized and available.

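### Inclusion criterion 13 can be met by willingness to be vaccinated, which is weaker than Section 12.2.1, and no sentence expressly withholds BCX9930 when the first vaccine dose was missed or late

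*Protocol*

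**What the plan says.** Protocol Section 8.1 opens with "Subjects must meet all of the following inclusion criteria (where applicable) prior to first dose of BCX9930 on Day 1 or specified time below". Criterion 13 then lists documented current vaccination against *N. meningitidis* A, C, W and Y and *S. pneumoniae*, followed by alternatives joined by *or*. The last alternative is "willingness to start vaccination series for any of the missing protocol required vaccines at least 14 days prior to Day 1 per Section 12.2.1". The synopsis version reads "or willingness to start vaccination series at least 14 days prior to Day 1" and does not refer to Section 12.2.1.

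Section 5.5.1 identifies life-threatening or fatal meningococcal infection as the most significant risk of complement inhibitors and states that "infection risk will be mitigated by requiring subjects to have up-to-date vaccinations against appropriate bacterial strains".

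Section 12.2.1 sets out the vaccination requirements:

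- For the same organisms, "Effective and current vaccination coverage must be documented for" is the opening of the rule.
- For subjects lacking a vaccine, "administration of any needed vaccines should start no later than 14 days prior to Day 1".
- Where a series needs more than one dose, "additional dose(s) may be administered after Day 1 to complete the recommended vaccination coverage".
- Problems of supply have their own route: "If a vaccine is not available, the sponsor medical monitor (or designee) should be contacted to discuss potential options", and the stated aim of that contact is to settle eligibility before the Day 1 visit is completed.

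Section 11.3.1 has the site confirm vaccination at screening and either give the required vaccines or schedule them with a local provider before Day 1. It also requires screening procedures to be finished and approved by the investigator before dosing. Sections 11.3.3 and 12.2 repeat the review of eligibility criteria and of medical and medication history on Day 1.

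**The concern.** Willingness is an attitude at screening, not an event that can be verified on Day 1. By Day 1 the 14-day point has passed, and the first dose either was given in time or was not. A criterion that must be met before dosing should say which of these it needs.

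The stake is the main stated mitigation for a potentially fatal infection. The back-up measures are permissive: Sections 5.5.1, 9.1 and 12.2.1 allow antibiotic prophylaxis but do not require it after a late vaccine. Up to 7 C3G subjects may also be taking mycophenolate, which Section 9.1 gives as an example of a drug that raises infection risk. If sites read the willingness clause differently, a subject whose vaccination appointment fell through could be held back at one site and dosed at another.

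**Working it through.** The plan gives no figure to reproduce on this point. The check sets the relevant sections side by side and then asks whether a stricter rule fits the screening window.

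**The rule, section by section**

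| Place | What it requires | Time point | Stated consequence if unmet |
|---|---|---|---|
| 8.1, criterion 13 | Documentation, or being vaccinated, or willingness to start (3 alternatives) | Start at least 14 days before Day 1 | Generic: all criteria before first dose |
| Synopsis, criterion 13 | Documentation, or willingness to start (2 alternatives) | Same | Same; no link to 12.2.1 |
| 12.2.1, documentation | Mandatory (*must*) | None given | None given |
| 12.2.1, first dose of a missing vaccine | Worded as *should* | By 14 days before Day 1 | None given |
| 12.2.1, unavailable vaccine | Contact the medical monitor | Before Day 1 is completed | Treated as an eligibility matter |
| 11.3.1, screening | Vaccinate or schedule | Before Day 1; no 14-day figure in this step | Generic: screening approved before dosing |
| 11.3.3 and 12.2, Day 1 | Review eligibility and history | Day 1 | Generic; no first-dose date check listed |

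**A worked case.** A subject lacks the meningococcal vaccine at screening, agrees to have it, and the site books an appointment. The appointment is missed, or the dose is given 5 days before Day 1. On Day 1 the site reviews criterion 13. One site reasons that the subject can no longer start 14 days ahead and holds the drug. Another reasons that the subject was willing and an appointment was made, and accepts the criterion. Section 12.2.1 favors the first reading, but its timing sentence says *should* and does not say what follows from a late dose. The medical-monitor route does not apply, because the vaccine was available.

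**Comparison within the protocol.** The Day 1 list in Section 11.3.3 makes a recorded negative urine pregnancy test an express condition of receiving study drug. Vaccination has no equivalent sentence.

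**Does a strict rule fit the window?**

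Inputs: screening window 56 days, extension up to 28 days with medical-monitor approval (Sections 11.3.1 and 11.3.2), and a vaccine interval of 14 days (criterion 13 and Section 12.2.1). Days are counted from the start of screening.

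- Outer limit: 56 + 28 = 84 days.
- Time to give the first dose and keep the interval: 56 − 14 = 42 days, or 84 − 14 = 70 days with the extension.
- If the first dose is given *k* days before the planned Day 1 (*k* from 0 to 13), the delay is 14 − *k* days: 14 days for *k* = 0, 7 for *k* = 7, 1 for *k* = 13.
- If Day 1 was planned for screening day *s*, the new Day 1 is *s* + 14 − *k*. It stays within 84 when *s* ≤ 70 + *k*, so with the full delay (*k* = 0) when *s* ≤ 70.

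| Planned Day 1 (*s*) | First dose given | New Day 1 | Against the 84-day limit |
|---|---|---|---|
| 56 | same day (*k* = 0) | 56 + 14 = 70 | 14 days to spare, extension needed |
| 70 | same day | 70 + 14 = 84 | at the limit |
| 84 | same day | 84 + 14 = 98 | 14 days over |

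**The case against.** The strongest reply is that the sections, read together, already supply the condition. Inclusion criteria must be met before the first dose. Criterion 13 in Section 8.1 incorporates Section 12.2.1, which makes documentation mandatory, sets the 14-day start, and expressly defers only additional doses beyond Day 1. If even an unavailable vaccine has to be resolved before Day 1 is completed, a merely missed one is hardly waived. The time limit is also built into criterion 13, since a subject with no first dose by Day 1 can no longer start 14 days ahead. This protocol uses *should* for instructions that are plainly binding, such as refraining from prohibited medications in Section 9.2.

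Much of this stands. It rules out three stronger readings that a reader might infer:

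- *That the protocol does not require a first dose.* Sections 8.1, 11.3.1 and 12.2.1 together show that one is intended by 14 days before Day 1.
- *That criterion 13 contradicts Section 12.2.1.* Both have two tracks, existing coverage or a timely start. The criterion is the weaker statement, not an opposite one.
- *That Day 1 does not recheck vaccination.* The eligibility review covers criterion 13 directly, and the history review covers the item under which vaccination was confirmed at screening.

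The reply does not remove the remaining gap. The Day 1 review returns the site to a criterion that willingness can literally satisfy, the documentation rule carries no time point, and the reader has to infer that a late dose stops dosing. The synopsis lacks even the cross-reference. Clear intent is a reason to make the operative sentence match it.

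**Conclusion.** The concern holds as a weakness in the stated eligibility rule. Criterion 13 asks for less than Section 12.2.1, and no sentence expressly withholds BCX9930 after a missed or late first dose. It should be corrected because it governs the main mitigation of the most serious class risk.

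Its size cannot be put as a rate, since the documents do not say how often scheduled vaccinations would be missed. A reader might infer that someone was dosed without timely vaccination, but nothing in the documents shows this. SAP Section 4.1 records that no subject enrolled under Version 4.0 before the program stopped, so the point concerns the text and any reuse of it.

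The conclusion rests on a literal reading of criterion 13. The delay figures assume that the late first dose is given no later than the planned Day 1; a dose given after that would push Day 1 back further.

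**What to change.** Reword criterion 13 in Section 8.1 and the synopsis to require either documented current vaccination, or a documented first dose (vaccine and date) of each missing required vaccine, meningococcal A, C, W, Y and pneumococcal, given at least 14 days before Day 1. In Section 12.2.1, change *should start* to *must start*. In Section 11.3.3, list the first-dose date as part of the Day 1 eligibility review. Keep the medical-monitor route for unavailable vaccines, keep allowing later doses of a series after Day 1, and leave the meningococcal B and Hib recommendations as they are.

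The change is to wording only and adds no visit or test. The cost is an occasional Day 1 delay of up to 14 days. A planned Day 1 up to screening day 70 can absorb this, using the medical-monitor-approved extension where needed. Beyond day 70, the full delay exceeds the 84-day limit and the subject may need rescreening, which Section 11.3.2 permits where eligibility can reasonably be expected.
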